Inclusion of Incarcerated Individuals: Incarcerated individuals will not be included in this study.

Inclusion of Minorities: We anticipate the racial-ethnic composition of the study sample to reflect that of the clinical population. If the proportion of minority women falls significantly below this anticipated number, we will consider targeted recruitment procedures to achieve the projected representation.

5. Number of Subjects

Up to 75 subjects seeking prenatal care at the University of New Mexico will be enrolled. Subjects will be pregnant, age 18 years or older, and registered as outpatients. Pregnant women are included because the purpose of this study is to determine the feasibility of studying the use of an oral probiotic agent in healthy, low risk, GBS positive pregnant women at term. We also propose to explore the effect of the probiotic on maternal GI symptoms and identify significant barriers to probiotic use in our population. Other special classes of subjects such as children, prisoners, and institutionalized individuals will not be enrolled.

This includes low risk patients seeking prenatal care at the University of New Mexico. Approximately 1500 women received prenatal care in the UNM Midwifery and OBGYN clinics in 2019 and approximately 20% were colonized with GBS. This gives us an adequate population from which to draw our study sample. We anticipate screening approximately 150 subjects over 8 months to allow us to enroll up to 75 subjects for our study after screening failures. A 30% dropout rate has been incorporated into sample size estimation to account for development of risk factors or failure to follow study procedures. These estimates are derived from Marquette University's randomized control trial pilot study of probiotics in pregnancy conducted at Marquette University and their current NIH funded double-blind randomized-controlled trial of Florajen3 to reduce GBS antenatal colonization. Tricore Lab has verified a 20% positive rate of GBS in our prenatal study population. For this open-label randomized control trial and feasibility study, a total sample of up to 75 participants will be targeted for enrollment and will be randomized to either the intervention group (receiving probiotics) or routine care (no intervention). A 30% dropout rate is assumed based on a preliminary study conducted at Marquette University; therefore, we anticipate that approximately 50 participants will

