Page 10 of 31 Version Date: 12/2/2021

complete the study.

6. Study Timelines

Procedures and Timing: Data will be collected for all subjects at five time points: T1 baseline (36.0-37.6 weeks), T2 (on labor admission), T3 (postpartum day 0-14), T4 (2 weeks postpartum), and T5 (6 weeks postpartum) as indicated in the table below.

Following informed consent, participants will have their first study visit at 36.0-37.6 weeks gestation (T1), during which baseline data will be collected and each subject will complete several brief questionnaires. Participants will be randomized into intervention group or routine care. The research staff member will sequentially distribute one prelabeled bottle of 30 probiotic capsules to the intervention group at time of enrollment. The bottle number will be used as the subject's number for the remainder of the study. Subjects in the control group will not receive any capsules and will be advised to continue their routine prenatal self-care. All subjects in the intervention group will be instructed to keep the study bottle in the refrigerator and to take one capsule per day until they give birth and to bring the bottle with them to the hospital at the time of labor. The PI, co-investigators, research staff, prenatal providers, and the subjects will not be blinded to group assignment.

The GBS vaginal to rectal swab collection procedure will be repeated for the both the intervention and routine care groups at T2 on labor admission. All participants will receive routine IAP per protocol as per CDC guidelines. At T3, the research staff will complete data collection with every participant during postpartum days 0-14; this will involve counting any remaining capsules in the study bottle, administering the study questionnaires, providing each subject with the first thank you merchandise card, and conducting a record review to document birth characteristics and IAP treatment. Adverse events will be solicited at each prenatal visit and via formal questionnaire for participants at T3-T5. Adverse events will be solicited at each prenatal visit and via formal questionnaire at T4-T5 for the newborn(s). A second merchandise card will be provided at T5.

Page 11 of 31 Version Date: 12/2/2021

Summary of Study Data Collection, Variables, Measures, and Timing

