Secondary outcomes include intervention adherence, maternal gastrointestinal (GI)

Page 14 of 31 Version Date: 12/2/2021

symptoms, and maternal and infant adverse events, at the 6 week postpartum visit.

8. Research Setting

The study will be performed at the University of New Mexico (UNMH) Women's Care Clinic, Women's Health Clinic, First Choice Community Healthcare clinics, and Maternity and Family Planning Clinic. Potential subjects will be screened and recruited in the UNMH clinics. After recruitment, they will undergo the consent process, and fill out initial questionnaires in the outpatient offices or over the phone. Upon labor admission to L&D, a GBS swab will be taken for study participants in addition to what is routinely collected for standard of care. There will be no involvement of any community advisory board. There will not be any research conducted outside of the UNM HSC.

9. Resources Available

[name], CNM fills a leadership role in the Department of OBGYN as the Associate Chief of the Midwifery Division. She has completed a Master's in Public Health and has conducted a successful research project, submitted through the UNM IRB This study resulted in a published manuscript in the Journal of Midwifery and Women's Health. In addition, the topic of this current research project was her Master's Thesis work for her Masters of Science in Nursing. She regularly lectures at the College of Nursing on the topic of GBS. [name], CNM will serve as a co-investigator for the current study. As a member of the Midwifery Division, [name] has collaborated on various studies including her role as co-investigator for the UNM APPLE study. She also collaborated on a recent study with Tricore lab, and has an excellent working relationship with the lab, who will work with us on this study. The other UNM co-investigators are part of the Midwifery Division and have collaborated on various studies with the OBGYN Department and Midwifery Division. We will also use the assistance of a medical student on our research team, who has participated in research studies in the past.

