At the time of labor admission to Labor and Delivery, participants will receive a vaginal-rectal GBS swab as a part of the research study. This is not standard of care and thus participants will receive this in addition to the standard of care. The results of the GBS swab will be collected for study purposes only.

All participants regardless of group assignment will receive the usual standard of care for GBS positive status and will be given intrapartum antibiotic prophylaxis (IAP) per protocol during labor.

All participants on postpartum day 0-14, in the hospital will answer these questionnaires: Antepartum Gastrointestinal Symptom Assessment (AP-GI-SA-10), Adverse Event Solicitation and Documentation Form (only for themselves, not their newborn(s)) and Questionnaire for Participants.

*we will not collect Adverse Event Solicitation and Documentation during this study time point because if the information is collected on postpartum day 0, there would be no way of reporting an adverse event for the newborn(s) at this time.

For the intervention group on postpartum day 0-14, study staff will conduct a final capsule count.

All participants at their 2 weeks postpartum visit will have an Adverse Event Solicitation and Documentation Form completed which will also include Adverse Event Solicitation and Documentation for their newborn(s).

Page 17 of 31 Version Date: 12/2/2021

All participants at their 6 weeks postpartum visit will have an Adverse Event Solicitation and Documentation Form & Future Feasibility Form completed which will also include Adverse Event Solicitation and Documentation for their newborn(s).

13. Data Analysis

Demographic characteristics for the full sample and each group will be presented. Logistic regression will be used to identify if the group assignments have relationships to variables such as demographic characteristics, hygiene practices, adherence, and birth characteristics. Logistic regressions test if any of these variables can predict the group that the participants were in. Another advantage of logistic regression is that by adding all the predictors at the same time, we can state the effect of each one controlling for the other predictors, presenting a stronger test of group independence.

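### Newborn adverse events are left out at T3 for a reason that fits only day 0, so a newborn whose mother completes neither T4 nor T5 has no planned adverse event record

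*Combined protocol and SAP*

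**What the plan says.** Section 7 lists among the secondary outcomes "symptoms, and maternal and infant adverse events, at the 6 week postpartum visit". Section 3 makes it an aim to learn whether any adverse events occur.

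Section 6 sets the contacts: T3 on postpartum days 0 to 14, T4 at 2 weeks and T5 at 6 weeks. Mothers are asked about their own adverse events by questionnaire at T3, T4 and T5. For newborns the questionnaire is used at T4 and T5 only. The same sentence also lists prenatal visits for the newborn, but these come before birth.

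Section 12 agrees. At T3 the mother completes the adverse event form for herself and not for her newborn, and a footnote explains that on day 0 "there would be no way of reporting an adverse event for the newborn(s) at this time".

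Staff also review records at T3, described in Section 6 as "conducting a record review to document birth characteristics and IAP treatment". Section 25 lists the birth characteristics. The newborn items are weight, length, head circumference and Apgar scores at 1, 5 and 10 minutes, all from the maternal record.

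On loss, Section 5 states: "A 30% dropout rate is assumed based on a preliminary study conducted at Marquette University". It expects about 50 of up to 75 participants to complete.

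**The concern.** The disease behind the trial is early-onset GBS disease of the newborn (Section 2), so events in the first days of life matter to its safety record. T3 is the study contact closest to the birth, and Section 12 places its questionnaires in the hospital. It is also the one postpartum contact that skips the newborn.

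The footnote's reason concerns a form completed on the day of birth. It is a good reason to ask again later. It does not explain why nothing is asked on days 1 to 14, or why a record review already under way does not look for newborn illness.

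Two things are at stake. Some newborns may have no adverse event record at all. For the rest, a birth-stay event is recorded only if the mother recalls and reports it two to six weeks later. The monthly safety review in Section 14 works from the adverse event questionnaires, so the planned forms bring no newborn event to that review before T4, even in retained families.

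**Working it through.** **1. Which planned source would capture a newborn event during the birth stay?**

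| Source | Section | Captures it? |
|---|---|---|
| T3 adverse event form | 12 | No, mother only |
| T3 record review | 6, 25 | Only birth measurements and Apgar scores to 10 minutes; no later illness, sepsis evaluation or admission is named |
| T4 form | 6, 12 | Yes, by recall, if T4 is completed |
| T5 form | 6, 12 | Yes, by recall, if T5 is completed |
| Provider solicitation at patient encounters; alert for unexpected events | 14 | Possibly, but the newborn is not named and no newborn form or time point is given |

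The gap in systematic collection is therefore the set of newborns whose mothers complete neither T4 nor T5. Completing either one closes it, subject to recall.

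**2. The plan's own dropout figure.** Inputs from Section 5: up to 75 enrolled, 30% dropout, about 50 completers.

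- 75 × (1 − 0.30) = 52.5, which agrees with about 50.
- Planned loss: 75 × 0.30 = 22.5, or about 23. Using 50 completers, it is 75 − 50 = 25.

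Section 5 attributes this dropout to emerging risk factors or failure to follow procedures and does not split it by time point. It is not a rate of missing both T4 and T5.

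**3. Size under an assumed rate of missing both contacts.** Multiple gestation is excluded (Section 4), so there is one newborn per mother. The 10% and 20% rates are assumptions; 30% borrows the overall dropout as a ceiling. The last column is the exact one-sided 95% upper limit on the event rate if no event is seen among n newborns, 1 − 0.05^(1/n).

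| Assumed rate | Newborns without a record | Newborns with a record (n) | Upper limit |
|---|---|---|---|
| 0% | 0 | 75 | 3.9% |
| 10% | 7.5, about 8 | 67 | 4.4% |
| 20% | 15 | 60 | 4.9% |
| 30% | 22.5, about 23 | 52 | 5.6% |

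For an assumed newborn event rate of 2%, the chance of seeing at least one event, 1 − 0.98^n, is 78% for n = 75, 74% for 67, 70% for 60 and 65% for 52. These figures take loss to be unrelated to newborn illness.

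**The case against.** The plan discloses the choice, gives a reason and schedules two later newborn assessments. Section 12 places the T3 questionnaires in the hospital, so many will be completed very early, and the end of the T3 window coincides with T4. For a mother who reaches T4, deferring the newborn questions loses little beyond recall. Questionnaires can be completed by phone (Section 16), telephone interviews are foreseen (Section 21), and a second merchandise card is paid for completing the 6-week visit (Section 23). Section 14 leaves an informal route for unexpected events. The Summary Data Collection Form and the adverse event form are not in the documents, so newborn fields on them cannot be ruled out.

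Most of this stands, and it limits the reach of the point. A reader might infer that birth-stay events are missed for every mother lost to follow-up. The documents do not support that: a mother seen or phoned at either T4 or T5 can still report them. A reader might also take about 23 of 75 as the expected loss. It is only a ceiling, because the 30% is not a postpartum rate. Nor do the documents show that mothers of ill newborns attend less, or that loss differs between arms. Both are plausible in an open-label trial where only one arm has a capsule regimen to follow, but mothers of ill infants could equally have more contact with the hospital.

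What remains is that no described source provides a newborn adverse event record when both contacts are missed, and that the day-0 reason does not justify leaving newborn illness out of the record review.

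**Conclusion.** The point holds for newborns whose mothers complete neither T4 nor T5: they have no planned adverse event record. Birth-stay events in all other newborns rest on maternal recall at T4 or T5. The number affected cannot be derived from the documents. It is about 8, 15 or 23 of 75 if 10%, 20% or 30% of mothers miss both contacts, and the last is a ceiling. With no events seen, coverage of 52 rather than 75 newborns would raise the upper limit on the event rate from 3.9% to 5.6%. No sample size or power figure is affected, and no direction of bias is established. The change should be made because it improves a secondary safety outcome at small cost.

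**What to change.** Remove the newborn exclusion at T3 in Sections 6 and 12. At the existing T3 record review, add a few fields for newborn events during the birth stay, for example NICU admission, sepsis evaluation, positive culture and death. Complete them for every randomised woman who has not withdrawn permission for record access, whether or not she completes T4 or T5. Keep the maternal reports at T4 and T5, which cover events after discharge. In the results, state for each arm how many newborns have a record-based entry, a maternal report, both or neither.

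The change needs no new visit or procedure. It costs minor coordinator time and an IRB modification. Section 25 describes the newborn items as coming from the maternal record, so consent and HIPAA wording for the infant's own record will be needed if it is not already covered; the consent form was not available to check. Section 16 already provides for storing neonatal adverse event data. One limit remains: Section 15 keeps only data collected up to withdrawal, so newborns of women who withdraw before birth may still have no record.

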For the continuous variables measured more than a single time (i.e. GI symptoms) the data analysis method will be latent change score model (LCM). This allows us to estimate the mean and standard deviation of the change between time points. By adding the group into the LCM, we will test the group mean difference in the change over time between the treatment and placebo groups. This will test the significance and clinical relevance (effect size) of the treatment over time. For the binary variable (qualitative GBS colonization), we will use logistic regression, with the baseline GBS colonization and treatment group as predictors. This would allow to test differences in the likelihood of being GBS positive, controlling for their initial status. The clinical relevance can be evaluated with the effect size Odds Ratio. For all the analyses, relevant demographic characteristics, hygiene practices, adherence, and birth characteristics identified in the first step will be added as covariates, to account for their possible influence in outcomes of interest.

14. Provisions to Monitor the Data to Ensure the Safety of Subjects

Risk Management and Emergency Response. If any study participant has a fever or other signs of infection, they will be instructed to contact the clinic or OB Triage, as is the usual process for pregnant women. Subjects will be provided with the PI contact information in the event that they need to call after hours. In the case of emergency, such as severe illness, the subjects will be instructed to call OB Triage and seek care in the University of New Mexico system whenever possible. Patient participation in the research study will be noted in the antenatal problem list; any healthcare provider who cares for the patient will have knowledge of study participation. Although highly unlikely, if it is determined that a subject has a clinical infection due to any component of Florajen Digestion Howaru® Dophilus-Lactobacillus acidophilus NCFMTM; Lactobacillus acidophilus La-14; floraFIT Bifidobacterium lactis Bi-07TM; Bifidobacterium animalis ssp. Lactis HN019, floraFIT Bifidobacterium longum Bl-05TM, as determined by culture and strain-typing, standard medical care will be provided to

Page 18 of 31 Version Date: 12/2/2021

the subject. No such emergencies occurred during the pilot testing or during NIH/NICHD funding R21HD095320 that is in progress under IND#16549 at the time of this application.

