The research staff will be responsible for the informed consent process, including discussion of the study and the subject's role in the study, and for answers to any questions posed by the subject. Once the subject indicates understanding, comprehension will be verified by asking the subject to explain the basics of the study, including the participant's role and possible risks and benefits. The informed consent will be signed or e-signed by the participant and the research coordinator. A copy of the signed or e-signed consent will be given to the participant and a copy will be securely stored by the research coordinator. Patient participation will be noted in the electronic medical record antenatal problem list in order to identify participants for collection at the time of labor.

They will have multiple opportunities to ask any questions that they may have, and they will also be provided with the clinic's contact information to get in touch with research investigators to address any additional questions or concerns.

Subjects will be reassured that participation is completely voluntary and does not affect their treatment, their relationship with their providers, or the university to minimize the possibility of coercion or undue influence. The patients will be asked that they understand the opportunity to participate and their complete freedom to decline. This will also be asked if they understand and if they have any questions. There is no minimum time period needed between informing the patient of the study and time of consent. Subject will be encouraged to take as much time as they need.

This study will obtain HIPAA authorization prior to enrollment. HIPAA authorization is embedded within the study consent form, which will be reviewed with all participants by the study team member(s) obtaining consent. Specific information that will be obtained includes data on demographics (socioeconomic status, race and ethnicity), lifestyle

Page 25 of 31 Version Date: 12/2/2021

practices (sexual practices, hygiene, and diet), and birth characteristics (mode of birth, whether the membranes were ruptured or not prior to the GBS swab, birth weight, birth length, head circumference, Apgar scores at 1, 5, and 10 minutes, which are all included in the maternal medical record).

Spanish speaking patients will be included. We will submit the translated documents once the study is approved by the IRB.

Cognitively Impaired Adults will not be included in the study.

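### Section 13 tests birth characteristics as predictors of study arm and then adjusts for them, and specifies no by-arm estimate of these post-randomisation measures

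*Combined protocol and SAP*

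**What the plan says.** Section 13 (Data Analysis) works in two steps.

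- **Step 1.** "Logistic regression will be used to identify if the group assignments have relationships to variables such as demographic characteristics, hygiene practices, adherence, and birth characteristics". Arm is the dependent variable: "Logistic regressions test if any of these variables can predict the group that the participants were in". Simultaneous entry is presented as an advantage: "by adding all the predictors at the same time, we can state the effect of each one controlling for the other predictors". The section credits this approach with "presenting a stronger test of group independence".
- **Step 2.** In all the outcome analyses, "relevant demographic characteristics, hygiene practices, adherence, and birth characteristics identified in the first step will be added as covariates".

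Section 25 (Consent Process) says what birth characteristics are: "mode of birth, whether the membranes were ruptured or not prior to the GBS swab, birth weight, birth length, head circumference, Apgar scores". Section 6 (Study Timelines) has them taken from a record review after birth.

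Section 1 (Objectives) lists them as further data to collect, apart from the outcomes, and Section 7 (Study Endpoints) does not mention them. The secondary outcomes do include "maternal and infant adverse events". The only by-group presentation that Section 13 promises is for demographic characteristics, and the only outcomes it gives a model for are the repeated continuous measures (GI symptoms) and GBS colonisation.

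**The concern.** A balance check asks whether randomisation produced comparable groups, so it belongs to variables fixed before randomisation. Sections 6 and 12 have the intervention group taking one capsule daily from enrolment until birth. Mode of birth, birth weight, length, head circumference and Apgar scores all come after that, so a difference between arms in any of them is chance or an effect of the product.

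Step 1 gives such a difference a different meaning, a failure of group independence. Step 2 then makes it an adjustment term in the GBS and GI-symptom models. Neither step yields an estimate of how much birth weight, mode of birth or Apgar differed between arms.

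Whether adverse events are identified is a stated aim (Sections 1 and 3), and the product has two more species than its predecessor (Sections 2 and 33). The birth record is an objective source that does not depend on a mother completing a later form. At stake is the completeness of the maternal and newborn safety description. The adjustment step also brings post-randomisation variables into the efficacy models.

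**Working it through.** **1. Role of the variables.** The documents state no figure for any birth measure, so there is none to reproduce. Setting the sections side by side:

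| Place | Treatment of birth characteristics |
|---|---|
| Section 1 | Further data collected, not an outcome |
| Section 6 | Record review after birth |
| Section 7 | Absent |
| Section 13, step 1 | Predictors of arm, with demographics, hygiene and adherence |
| Section 13, step 2 | Covariates in all outcome models, if identified in step 1 |
| Section 14 | Absent; monthly safety reports draw on the adverse event questionnaires |

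No entry compares them between arms as outcomes.

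**2. Adverse-event route.** Newborn events are solicited by form at T4 and T5 (Section 6). Section 12 has no newborn form at T3. Section 14 has providers solicit events that are not pregnancy related, and Section 13 names no analysis of adverse events. A newborn problem that someone recognises and records has a route. A shift in birth weight, Apgar or caesarean frequency that nobody records as an event does not.

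**3. Sample size for illustration.** Up to 75 enrolled and 30% dropout (Section 5): 75 × 0.70 = 52.5, consistent with the approximately 50 completers stated. I take 25 to 26 per arm. Equal allocation and two-sided 0.05 are assumptions.

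**4. One measure compared directly.** Normal approximation: power = Φ(d√(n/2) − 1.96).

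- d = 0.8, n = 25: Φ(2.83 − 1.96) = 0.81
- d = 0.8, n = 26: Φ(2.88 − 1.96) = 0.82
- d = 0.5, n = 25: Φ(1.77 − 1.96) = 0.42
- d = 0.5, n = 26: Φ(1.80 − 1.96) = 0.44

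**5. The same measures entered jointly.** Simulation with 26 per arm, three normal size measures (standing for weight, length and head circumference) all shifted by 0.8 SD, and p < 0.05. Shift and correlations are assumptions. Proportion of runs flagged:

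| Correlation | 0.5 | 0.7 | 0.8 |
|---|---|---|---|
| Each measure alone (t-test) | 0.80–0.82 | 0.80–0.82 | 0.80–0.82 |
| Each coefficient, three measures in the model | 0.17 | 0.09 | 0.08 |
| Each coefficient, plus 8 unrelated predictors | 0.18 | 0.12 | 0.10 |
| Any of three, compared singly | 0.95 | 0.93 | 0.90 |
| Any of three coefficients, three in the model | 0.47 | 0.27 | 0.21 |
| Any of three coefficients, plus 8 unrelated | 0.48 | 0.34 | 0.27 |
| Overall likelihood-ratio test, three in the model | 0.85 | 0.77 | 0.74 |
| Overall likelihood-ratio test, plus 8 unrelated | 0.70 | 0.61 | 0.59 |

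Repeat runs put the lowest per-coefficient value at 0.07, hence 7–18%. With no true shift, the overall test rejects in about 0.07 of runs (three predictors) and 0.11–0.13 (eleven), so its larger-model figures are somewhat inflated. Three unadjusted single comparisons flag at least one measure in about 0.10–0.12 of null runs.

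**6. Adherence in the same model.** Section 6 measures adherence in the probiotic group only. If it is entered as Section 13 lists it and coded 0 for controls (an assumption), it separates the arms completely. In simulation the joint model then gave no usable fit in any run.

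**The case against.** The case on the other side has four parts.

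- **An association is symmetric.** Arm on birth weight and birth weight on arm carry the same association, and Section 13 says the effect of each predictor can be stated. It also speaks of regressions in the plural, so separate models are not excluded. This stands in part: step 1 would produce some information. But it would be an odds ratio for arm membership, adjusted for the other predictors if entered jointly, and presented as evidence on balance.
- **The per-coefficient figures are not the whole joint model.** A reader might infer that a real shift would mostly go unflagged. The documents do not support that, because they do not say which test decides. The overall test detects the assumed shift in roughly 59–85% of runs. The low figures apply only when coefficients are read one at a time.
- **A safety route exists.** A reader might infer that an effect on the newborn could never be reported as safety. That goes too far: infant adverse events are a secondary outcome, solicited at T4 and T5, with monthly review. The gap is confined to shifts not recorded as events.
- **Scale.** This is a feasibility pilot with about 50 completers, the documents never name birth characteristics as safety measures, and the 0.8 SD shift is not theirs. At 0.5 SD even the direct comparison flags only 42–44%. This stands, and it is why the remedy should be estimates with intervals and not tests.

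None of these gives the plan a by-arm estimate of the birth measures or justifies adjusting for them.

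**Conclusion.** The point holds. Section 13 assigns post-randomisation birth measures to a balance test and then to the covariate set, and no section specifies a by-arm estimate. It would be wrong to say that they are analysed only as predictors of arm: the covariate step is a second use, and a second problem. Mode of birth and Apgar scores are also settled after the admission swab, so adjusting the GBS result for them has no clear rationale.

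The structural conclusion rests on the text alone. The numerical part rests on assumed values: 26 per arm, 0.8 SD in all three size measures, correlation 0.5 to 0.8. Under them, joint entry lowers the chance of flagging a given measure from about 80% to about 7–18%, so the claim of a stronger test fails for individual measures. The overall test keeps much of its ability to detect the shift. The main consequence is an incomplete safety description, not a certainty that an effect would go unseen.

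**What to change.** - **Section 13:** remove birth characteristics from the group-prediction step and from the covariate set, and limit the balance description to baseline variables.
- **Section 7:** list mode of birth, birth weight, length, head circumference and Apgar scores as maternal and newborn safety outcomes.
- **Reporting:** give each measure separately by randomised arm, for every randomised woman with a birth record, as a difference with a 95% interval and no mutual adjustment. Label the table descriptive.

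The data are already to be collected, so the cost is one more table and a few sentences in Sections 7 and 13. The downside is several imprecise intervals at this sample size, which should not be read as formal tests or as evidence of no effect.
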